#### 5.2.10. Adequate Post-baseline Disease Assessment

An adequate disease assessment is defined as an assessment where a time-point response of sCR, CR, VGPR, PR, minimal response (MR), Stable Disease (SD) or PD has been provided. Timepoints where the response is not evaluable or no assessment was performed will not be used for determining the censoring date for time-to-event endpoints including PFS, DOR and DOCR.

#### 5.2.11. Nominal and Unscheduled Visits

For all algorithms and analyses, visit labels as specified on the CRF will be used as the nominal timepoint (ie, assessment will not be slotted).

Unless otherwise specified, unscheduled assessments will not be displayed in summary tables by nominal visit/timepoint. Unscheduled assessments will be used when deriving baseline and worst case on-treatment for safety and PRO analyses (except where noted for baseline ECGs). Additionally, unscheduled assessments will be used for efficacy analyses (eg, defining date of progression/censoring, best overall response, date of last contact).

## 5.2.12. Standard Deviations and Reporting Conventions

The following conversion factors will be used to convert days into weeks, months or years: 1 week = 7 days, 1 month = 30.4375 days, 1 year = 365.25 days.

Demographics and physical measurements:

- Age [years]: (year of given informed consent year of birth).
- The integer part of the calculated age will be used for reporting purposes.
- Body mass index (BMI)  $(kg/m^2) = weight (kg)/[height (m)]^2$ .

For reporting conventions, mean and median should generally be displayed 1 more decimal place than the raw data and standard deviation should be displayed to 2 more decimal places than the raw data. Percentages will be reported to 1 decimal place. The rounding will be performed to the closest integer/first decimal using the common mid-point between the 2 consecutive values. For example, 5.1 to 5.4 will be rounded to an integer of 5, and 5.5 to 5.9 will be rounded to an integer of 6.

## 5.2.13. Analyses for Continuous and Qualitative Variables

Continuous variables will be summarized using descriptive statistics ie, number of nonmissing values and number of missing values [ie, n (missing)], mean, median, standard deviation, minimum, maximum and first and third quartile (Q1 and Q3).

Qualitative variables will be summarized by frequency counts and percentages. Unless otherwise specified, the calculation of proportions will include the missing category. Therefore, counts of missing observations will be included in the denominator and presented as a separate category.

In case the analysis refers only to certain visits, percentages will be based on the number of participants still present in the study at that visit, unless otherwise specified.

## 5.2.14. Analyses for Time-to-Event Endpoints

Kaplan-Meier estimates (product-limit estimates) will be presented by cohort together with a summary of associated statistics including the median time with 2-sided 95% CIs. Probabilities of an event at particular timepoint will be estimated with corresponding 2-sided 95% CIs. The CI for the median will be calculated according to Brookmeyer and Crowley, 1982 and the CIs for the survival function estimates at particular timepoints will be derived using the log(-log) method.

If a cumulative incidence analysis is performed, the 25th, 50th, and 75th percentiles and probabilities of an event at particular points in time will be estimated from the cumulative incidence curve. Confidence intervals for the estimated probability of an event at a particular timepoint will be generated using the delta method with a log(-log) transformation for the standard error.

### 5.3. Methods to Manage Missing Data

Unless otherwise specified, all data will be evaluated as observed, and no imputation method for missing values will be used.

Any imputations will occur at the analysis dataset level. Additionally, in all data listings imputed values will be presented and flagged as imputed.

Missing statistics, eg, when they cannot be calculated, should be presented as 'ND' for not done, 'NR' for not reached or 'NA' for not applicable. For example, if N=1, the measure of variability cannot be computed and should be presented as 'ND' or 'NA'.

### 5.3.1. Missing Pharmacokinetic Data

### **Concentrations below the limit of quantification**

For all calculations and figures, all concentrations assayed as below the limit of quantification (BLQ) will be set to zero. The BLQ values will be excluded from calculations of geometric means and their CIs. A statement similar to 'All values reported as BLQ have been replaced with zero' will be included as a footnote to the appropriate tables and figures. In listings BLQ values will be reported as below limit of quantification ("<LLOQ"), where LLOQ will be replaced with the corresponding value from the analytical assay used.

#### Deviations, missing concentrations and anomalous values

In summary tables, concentrations will be set to missing if one of the following cases is true:

- A concentration has been reported as ND (ie, not done) or NS (ie, no sample);
- A deviation in sampling time is of sufficient concern or a concentration has been flagged as anomalous by the clinical pharmacologist.

At the discretion of the clinical pharmacologist, summary statistics may not be presented at a particular timepoint if more than 50% of the data are missing. For analysis of pharmacokinetic concentrations, no values will be imputed for missing data. If less than 3 evaluable concentrations or PK parameters at a given timepoint are available, only minimum and maximum will be presented.

## 5.3.2. Missing ECG Data

For QTc analyses, no values will be imputed for missing data. If 1 or 2 of the triplicate measurements for an ECG parameter are missed, the average of the remaining 2 measurements or the single measurement, respectively, can be used in the analyses. If all triplicate measurements are missing at a timepoint for an ECG parameter, no values will be imputed for this timepoint. If the triplicate needs to be repeated because of an artifact, then the repeated triplicate will be reported on an unscheduled CRF page. Based on a review of the data, these unscheduled assessments may be used in place of the assessments at the nominal time. Data review and consultation with the study team is required to flag these cases.

## 5.3.3. Handling of Incomplete or Missing Dates

## 5.3.3.1. Adverse Events

## AE Onset Date:

**AE Onset Date:** If the AE onset date is completely missing, and if the date of first dose is less than AE stop date, then the onset date will be assigned as the date of first dose. Otherwise if the date of first dose is after the AE stop date then the AE onset date will be imputed as the earliest of non-missing AE stop date or informed consent date.

**AE Stop Date:** If the AE stop date is completely missing then the stop date will be imputed as the latest of the participant withdrawal/completion date, death date, last dose of study intervention, or AE onset date.

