## 3.4. Baseline Variables

## Start and end dates of study intervention:

The date of first dose (start date) of study intervention is the earliest date of nonzero dosing of the study drug.

The date of last dose of study intervention is the latest date of nonzero dosing of the study drug.

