### 5.3.3.2. Exposure

No imputation will be done for the first dose date. Date of the last dose of study intervention, if unknown or partially unknown, will be imputed as follows:

- If the last date of study intervention is completely missing and there is no End of Treatment (EOT) CRF page and no death date, the participant should be considered to be ongoing and use the data cutoff date for the analysis as the last dosing date; or
- If the last date of study intervention is completely or partially missing and there is either an EOT CRF page or a death date available (on or prior to the data cutoff date), then impute this date as the last dose date:
  - = 31DECYYYY, if only Year is available and Year <Year of min (EOT date, death date),
  - = Last day of the month, if both Year and Month are available and Year = Year of min (EOT date, death date) and Month < the month of min (EOT date, death date), or
  - = min (EOT date, death date), for all other cases.

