# 6.7.1.1. Adverse Events of Special Interest

Adverse events of special interest (AESI) includes the following events:

- CRS: PT coded as "cytokine release syndrome" and collected on the AE CRF page;
- ICANS: PT coded as "immune effector cell-associated neurotoxicity syndrome" and collected on the AE CRF page;
- Peripheral neuropathy: Standardized MedDRA Queries (SMQ) Peripheral Neuropathy (narrow and broad excluding PTs included in the Guillain-Barre syndrome SMQ) and Guillain-Barre syndrome SMQ (narrow).

CRS and ICANS will be assessed according to ASTCT criteria. All the analyses will be performed for each individual AESI separately.

For CRS and ICANS, the 4 participants who received 44 mg priming dose will be summarized separately within each summary table.

A high-level summary of each AESI will include the number and percent of participants with, separately:

- Any AESI;
- Serious AESI;

- AESI by maximum toxicity grade;
- Had >1 AESI (for CRS and ICANS only);
  - Note: If there are >1 AESI with different grades between two doses, it will be considered as one event;
- Had ICANS concurrent with CRS (for ICANS only). Note: if both CRS and ICANS occurred between the same two doses they will be considered as concurrent;
- AESI leading to dose interruptions;
- AESI leading to dose reductions;
- AESI leading to dose interruptions or reductions;
- AESI leading to permanent discontinuation of study intervention;
- AESI with outcome as resolved.

In addition, the following summary will be provided with descriptive statistics as well as broken down in categories by the time to onset, resolution, and duration of the AESI:

- Time to onset of the AESI;
- Time to resolution of the AESI;
- Duration of each AESI event.

For CRS and ICANS, time relative to dose (ie, after the first dose, after the second dose, after the third dose, after >3 doses) will also be summarized with descriptive statistics.

A summary of AESI symptoms will be provided as follows. The most severe symptom will be summarized if participants have multiple occurrences of AESI symptoms.

- The CRS symptoms (fever, hypoxia and hypotension) as collected on the 'CRS AE' CRFs will be summarized by symptom grade using frequency counts and percentages;
- The ICANS symptoms as collected on the 'ICANS' CRFs will be summarized using frequency counts and percentages;

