# 6.7.1.2. Other Adverse Events of Clinical Interest

Other adverse events of clinical interests (oAECIs) include the following events:

- Infections:
  - The MedDRA SOC of Infections and infestations.
- Cytopenias:
  - The MedDRA PTs for cytopenias are defined in Appendix 2.
- Hypogammaglobulinemia:
  - Including the MedDRA PTs: Blood immunoglobulin G decreased, Hypogammaglobulinaemia, Hypoglobulinaemia, Immunoglobulins decreased and Globulins decreased.
- Injection site reactions:
  - The MedDRA HLT of Injection site reactions.
- Secondary malignancies:
  - The MedDRA SOC of Neoplasms Benign, Malignant and Unspecified.

All the analyses will be performed by each individual oAECI separately. For cytopenias, the individual PTs (ie, not clustered terms) will be reported in the summary.

A high-level summary of each of oAECI will be provided including the following, if applicable:

- Any oAECIs;
- Serious oAECIs;
- oAECIs by maximum toxicity grade;
- oAECIs leading to dose interruptions;
- oAECIs leading to dose reductions;
- oAECIs leading to dose interruptions or reductions;
- oAECIs leading to permanent discontinuation of study intervention.

The following summary will be provided for each oAECI, if applicable:

- oAECI by PT and maximum severity grade (all causality and treatment-related);
- Time to onset of the oAECI, time to resolution, and duration of the oAECI with descriptive statistics as well as broken down in categories.

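### The stop-date rule for adverse events does not separate ongoing events from ended events with an unknown date, so ongoing AESIs and oAECIs enter the duration and time-to-resolution summaries as completed

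*SAP*

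**What the plan says.** SAP 5.3.3.1 has one trigger: "If the AE stop date is completely missing then the stop date will be imputed". Where it applies, an event's "stop date will be imputed as the latest of the participant withdrawal/completion date, death date, last dose of study intervention, or AE onset date"; that is, the value assigned is the latest of four dates. The recorded outcome of the event plays no part, and neither the data cutoff nor the last-contact date is among the four.

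Related conventions:
- SAP 3.4: "The date of last dose of study intervention is the latest date of nonzero dosing of the study drug".
- SAP 5.3: "Unless otherwise specified, all data will be evaluated as observed, and no imputation method for missing values will be used". The stop-date rule is one of the cases specified otherwise.
- SAP 5.3 also says that "in all data listings imputed values will be presented and flagged as imputed". It promises no such flag in summary tables.

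SAP 6.7.1.1 asks, separately for CRS, ICANS and peripheral neuropathy, for time to onset, time to resolution and "Duration of each AESI event", as descriptive statistics and in categories. SAP 6.7.1.2 asks, where applicable, for "Time to onset of the oAECI, time to resolution, and duration of the oAECI with descriptive statistics" for infections, cytopenias, hypogammaglobulinaemia, injection site reactions and secondary malignancies. Neither section mentions censoring or limits these summaries to resolved events. SAP 6.7.1.1 separately counts AESIs whose recorded outcome is resolved; SAP 6.7.1.2 has no such count.

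**The concern.** An ongoing event normally has no stop date, so the trigger catches it together with ended events whose date was lost. The trial keeps following events after treatment. Protocol 8.3.1 collects them for at least 90 days after the last dose. Protocol 7.1 follows events persisting at the follow-up visit at least every 4 weeks until they resolve or no further improvement is expected. SAP 3.5 lets a treatment-emergent event start up to 90 days after the last dose. The sponsor can therefore hold data showing that an event persisted, while the analysis dataset closes it at the last dose.

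Elsewhere the SAP handles open-ended cases differently. SAP 5.3.3.2 has an ongoing branch for the last dose, SAP 5.3.3.4 sets the last dose to the cutoff for participants still on treatment, and SAP 5.3.3.5 leaves other completely missing dates alone.

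At stake is the description of how long the main toxicities last. The longest events are the likeliest to be open at the cutoff, so the error falls on persistent neuropathy, cytopenias and hypogammaglobulinaemia rather than evenly.

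**Working it through.** The documents give no duration figure to reproduce, so the check applies the rule to constructed cases.

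**Rule.** Stop = max(withdrawal or completion, death, last dose, onset), over the dates that exist (SAP 5.3.3.1). Duration = stop − onset + 1. The SAP gives no AE duration formula; the +1 is assumed from its PFS, DOR and treatment-duration formulas.

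**Single cases.** All day numbers are assumed. The event is never recorded as ended and the cutoff is Day 400.

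| Participant | Onset | Last dose | Imputed stop | Duration by the rule | Known duration |
|---|---|---|---|---|---|
| On treatment | 60 | 396 | 396 | 396 − 60 + 1 = 337 | at least 400 − 60 + 1 = 341 |
| On treatment, last dose set to cutoff (SAP 5.3.3.2) | 60 | 400 | 400 | 341 | at least 341 |
| Off treatment, in follow-up | 60 | 100 | 100 | 100 − 60 + 1 = 41 | at least 341 |
| Same, event seen only to 90 days after last dose | 60 | 100 | 100 | 41 | at least 190 − 60 + 1 = 131 |
| Off treatment, onset after last dose | 130 | 100 | 130 | 130 − 130 + 1 = 1 | at least 400 − 130 + 1 = 271 |
| Off treatment, died Day 300 | 60 | 100 | 300 | 241 | 241, unresolved |
| Off treatment, withdrew Day 250 | 60 | 100 | 250 | 191 | at least 191 |

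The severe shortening is confined to participants off treatment and still followed. In every row an unresolved event becomes a completed duration.

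**Illustrative simulations.** Event durations are exponential and every input is assumed.
- Set 1: median treatment 200 days, then a median of 300 days to death or withdrawal, cutoff between Day 360 and Day 720; 400,000 events, some starting after the last dose.
- Set 2: cutoff Day 450; last dose Day 446 if on treatment, otherwise uniform between Days 60 and 300; 25%, 50% or 75% off treatment and all of those in follow-up; no deaths or withdrawals; no onsets after the last dose.

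| True median (days) | Set 1: rule | Set 1: Kaplan-Meier | Set 2: rule | Set 2: Kaplan-Meier | Set 2: ongoing at cutoff |
|---|---|---|---|---|---|
| 90 | 69 | 91 | 81–86 | 89 | 8–11% |
| 180 | 100 | 181 | 114–150 | 179–181 | 28–31% |
| 365 | 122 | 365 | 124–192 | 363–371 | 53–56% |

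The Kaplan-Meier columns censor ongoing events and recover the true median closely. Shortfall under the rule:
- True median 90: 1 − 69/90 = 23% in set 1; 1 − 86/90 = 4% to 1 − 81/90 = 10% in set 2.
- True median 365: 1 − 122/365 = 67% in set 1; 1 − 192/365 = 47% to 1 − 124/365 = 66% in set 2.

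In set 1 about 25% of ongoing events in participants still followed receive exactly 1 day. That share depends on how many onsets are placed after the last dose.

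**The case against.** The best case for the plan has five parts.

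- **Intended scope.** The rule sits under incomplete or missing dates, the default is analysis as observed, and the outcome field shows that ongoing events can be identified. The sponsor may mean it only for lost dates, and the CRF is not available to check. This is possible, but the text states no such limit, and followed literally it closes ongoing events.
- **Cutoff branch.** SAP 5.3.3.2 covers a wholly absent last dose date where neither a death nor an end-of-treatment page has been recorded: "the participant should be considered to be ongoing and use the data cutoff date for the analysis as the last dosing date". This stands, and it is why the loss on treatment is small or nil. It does not help a participant who has stopped treatment.
- **Completion date.** The SAP does not say whether withdrawal or completion refers to treatment or to study; Protocol 7.1 and 7.2 list completion under both. On the study reading, participants should have one of these dates or a death date by the end of the study, so the severe shortening would be confined to earlier cutoffs. The planned final analysis can be one of these: Protocol 9.2 sets it by two post-baseline response assessments, whereas Protocol 4.4 requires at least 2 years of survival follow-up.
- **Resolved events.** The SAP does not say that unresolved events enter time to resolution, and resolved AESIs are counted by outcome. The first part is a fair ambiguity for time to resolution. It does not cover duration, which is asked for each AESI event without restriction.
- **Limited reach.** These are descriptive tables in a single-arm study, imputed dates are flagged in listings, and short events are affected less. All of this stands.

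A reader might also infer that the last dose is usually the imputed end, or that unresolved events in general are reported as short. The documents support neither. The rule takes the latest of four dates, and no figures are given for how many participants fall in each group.

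**Conclusion.** The point holds as a defect in a written rule. Ongoing AEs enter the AESI and oAECI duration summaries as completed events and, unless an unstated restriction applies, the time-to-resolution summaries too. The effect is small on treatment. After death or withdrawal the follow-up is not cut short, although the event still counts as finished. It is severe for participants off treatment but still in follow-up at the cutoff.

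The overall size cannot be fixed from the documents. It depends on how long events last and how many participants are off treatment and still followed. The two sets of assumptions agree in direction and in growing with persistence, but differ in amount, most visibly for shorter events.

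Incidence, grade, the count of resolved AESIs and the primary endpoint are not affected. It would go too far to say that the SAP counts unresolved AESIs as resolved, because that count rests on recorded outcome. The change should be made because it is cheap and because the durations of persistent toxicities would otherwise be understated.

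**What to change.** - In SAP 5.3.3.1, limit stop-date imputation to events recorded as ended with an unknown date, and keep ongoing events open. State whether withdrawal or completion means treatment or study.
- In SAP 6.7.1.1 and 6.7.1.2, summarise duration and time to resolution in one of two ways: by Kaplan-Meier, with ongoing events censored at the earliest of data cutoff, last contact or death; or for resolved events only, with the number ongoing shown beside them.
- Add a resolved/ongoing count for each oAECI.

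No new data are needed. Outcome is already used in SAP 6.7.1.1, last contact is derived in SAP 5.2.7 and Kaplan-Meier methods are set out in SAP 5.2.14. The cost is one rule and slightly more table programming. Kaplan-Meier has its own price: censoring at death assumes that death is non-informative for event duration, and repeated events in one participant are not independent. Resolved-only summaries avoid the censoring assumption but favour short events, so the number ongoing must be shown with them.

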### 5.3.3.2. Exposure

No imputation will be done for the first dose date. Date of the last dose of study intervention, if unknown or partially unknown, will be imputed as follows:

- If the last date of study intervention is completely missing and there is no End of Treatment (EOT) CRF page and no death date, the participant should be considered to be ongoing and use the data cutoff date for the analysis as the last dosing date; or
- If the last date of study intervention is completely or partially missing and there is either an EOT CRF page or a death date available (on or prior to the data cutoff date), then impute this date as the last dose date:
  - = 31DECYYYY, if only Year is available and Year <Year of min (EOT date, death date),
  - = Last day of the month, if both Year and Month are available and Year = Year of min (EOT date, death date) and Month < the month of min (EOT date, death date), or
  - = min (EOT date, death date), for all other cases.

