## 3.5. Safety Endpoints

Safety endpoints will be summarized based on the on-treatment period unless otherwise specified.

On-treatment period is defined as the time from the first dose of study intervention through the minimum of [90 days after last dose, or (start day of new anticancer therapy -1 day)]. Anticancer therapy includes drug therapy, stem cell transplant, and radiation with curative intent; the start of new anticancer therapy after the first dose of study intervention is derived as outlined in Section 5.2.6. Adverse events occurring on the same day as the first dose of study intervention will be considered to have occurred during the on-treatment period. All other assessments which occur on the same day as the first dose of study intervention will be considered baseline assessments (see Section 3.4 for the definition of baseline).

Safety data collected after the on-treatment period as described above will be listed but not summarized.

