MMM < Month of min [max(PD date + 1 day, last dose of study intervention + 1 day), end date of new anticancer therapy]

THEN imputed start date = DAY (Last day of MMM) MMM YYYY ;

• ELSE IF YYYY = Year of min [max(PD date + 1, last dose of study intervention + 1), end date of new anticancer therapy], AND

MMM = Month of min [max(PD date + 1 day, last dose of study intervention + 1 day), end date of new anticancer therapy]

THEN imputed start date = min [max(PD date + 1 day, last dose of study intervention + 1 day), end date of new anticancer therapy]);

• ELSE IF YYYY = Year of min [max(PD date + 1, last dose of study intervention + 1), end date of new anticancer therapy], AND

MMM > Month of min [max(PD date + 1 day, last dose of study intervention + 1 day), end date of new anticancer therapy]

THEN imputed start date = 01 MMM YYYY;

• ELSE IF YYYY < Year of min [max(PD date + 1, last dose of study intervention + 1), end date of new anticancer therapy]

THEN imputed start date = DAY (Last day of MMM) MMM YYYY;

• ELSE IF YYYY > Year of min [max(PD date + 1, last dose of study intervention + 1), end date of new anticancer therapy]

THEN imputed start date = 01 MMM YYYY.

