#### 6.6.3. Study Intervention Exposure

Exposure will be summarized based on the Safety Analysis Set.

Elranatamab is administered as a subcutaneous injection at 76 mg once every week on Days 1, 8, 15 and 21 of each 28-day cycle. Elranatamab is also administered on C1D4. A minimum of 2 days should be maintained between the 2 step-up priming doses (C1D1 and C1D4) and a minimum of 3 days between C1D4 dose and the first full dose (C1D8); a minimum of 6 days should be maintained between doses thereafter. The dose of elranatamab should be increased to 76 mg on C1D8 as long as the participant meets the criteria listed in Protocol Section 6.6.1. If a participant does not meet these criteria on C1D8, initiation of dosing with 76 mg should be deferred until the criteria are met. In addition, if a participant has received QW dosing for at least 6 cycles and has achieved an IMWG response category of PR or better persisting for at least 2 months, the dose interval will be changed from QW to Q2W. If the participant subsequently begins to have an increase of disease burden not yet qualifying as PD according to IMWG criteria, dose intervals should return to weekly dosing. If the dose interval is changed, cycles should remain the same length (ie, 4-week cycles).

The summary of treatment exposure elranatamab will include the following information:

• Treatment duration (months);

- Number of cycles started per participant (mean, median, min, max);
- Number and percent of participants starting a cycle (any cycle, 1, 2, 3, 4, 5, 6, 7, 8, 9, 10, 11, ≥12-<18, ≥18-<24, ≥24 cycles);
- Total cumulative dose (mg);
- Overall dose intensity (mg/week);
- Overall relative dose (%);
- Overall relative dose intensity (%);
- Number and percent of participants who received 44 mg on the C1D1 visit;
- Number and percent of participants who received 32 mg on the C1D4 visit;
- Number and percent of participants who received 76 mg on the C1D8 visit;
- Number and percent of participants after 6 cycles who switched from QW to Q2W;
- Number and percent of participants, among those switching from QW to Q2W, who switched back to QW.

The treatment duration of elranatamab (in weeks) during the study for a participant is defined as:

Treatment duration (months) = (last dose date – first dose date + 1)/30.4375

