#### 6.7.2. Deaths

The frequency (number and percentage) of participants in the Safety Analysis Set who died at any time, who died within 28 days of the first dose of study intervention, and who died within 90 days after last dose of study intervention as well as the primary reason for death, will be tabulated based on information from the 'Death Details' and 'Survival Follow-Up' CRFs.

Date and cause of death will be provided in individual participant data listing together with selected dosing information (date of first/last administration, dose).

In addition, deaths due to COVID-19 may be presented in a separate listing if there is significant impact of COVID-19.

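### The last-dose imputation sets a known month in an earlier calendar year to the EOT or death date, outside the recorded month

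*SAP*

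**What the plan says.** SAP 5.3.3.2 applies "If the last date of study intervention is completely or partially missing and there is either an EOT CRF page or a death date available", dated no later than the data cutoff. The reference date is the earlier of EOT and death, and there are three outcomes:

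1. "31DECYYYY, if only Year is available and Year <Year of min (EOT date, death date").
2. "Last day of the month, if both Year and Month are available and Year = Year of min (EOT date, death date"), with the further condition that the recorded month is before the reference month.
3. "min (EOT date, death date), for all other cases".

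SAP 5.3.3.4 deals with the corresponding problem for the start of new anticancer therapy. In its block for a known year and month it has a separate line, "ELSE IF YYYY < Year of min [max(PD date + 1, last dose of study intervention + 1), end date of new anticancer therapy"], which returns the last day of the recorded month.

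The last-dose date is then used in:

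- SAP 6.6.3: "Treatment duration (months) = (last dose date – first dose date + 1)/30.4375".
- SAP 3.5, where the on-treatment period ends at "the minimum of [90 days after last dose, or (start day of new anticancer therapy -1 day")].
- SAP 6.7.2, which counts participants "who died within 90 days after last dose of study intervention".
- SAP 5.3.3.4, where last dose plus one day is one term in the imputed start of new anticancer therapy.

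**The concern.** The second branch compares months only within one calendar year, and the first applies only when no month is recorded. A date with both year and month, in a year before the reference year, fits neither and is assigned the reference date. That date lies outside the recorded month.

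The rule also behaves perversely: with only the year on record it returns 31 December of that year, but adding the month moves the result later, into the next year.

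The error runs one way. The imputed last dose is always too late, so treatment duration is overstated. The 90-day limit that decides which adverse events are treatment-emergent, and which deaths count as within 90 days of last dose, can move out with it.

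**Working it through.** The plan states no figure on this point, so the check is to apply the rule as written to test dates and compare it with the month-end rule of SAP 5.3.3.4.

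**Which branch applies.** Take a last dose recorded as November 2021, EOT on 12 January 2022 and no earlier death.

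- Branch 1 needs the year alone to be known. The month is known, so it fails.
- Branch 2 needs the recorded year to equal the reference year. 2021 is not 2022, so it fails.
- Branch 3 applies and returns 12JAN2022.

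SAP 5.3.3.5 does not rescue the case, because it covers only dates not dealt with in the sections before it.

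**Size.** Excess = SAP result minus last day of the recorded month. Duration = (last dose − first dose + 1)/30.4375. All dates are illustrative, with an assumed first dose of 01JUN2021.

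| Recorded last dose | Earlier of EOT and death | SAP result | Month end | Excess (days) | Duration in months, SAP vs month end |
|---|---|---|---|---|---|
| NOV2021 | 12JAN2022 | 12JAN2022 | 30NOV2021 | 43 | 226/30.4375 = 7.43 vs 183/30.4375 = 6.01 |
| DEC2021 | 12JAN2022 | 12JAN2022 | 31DEC2021 | 12 | 226/30.4375 = 7.43 vs 214/30.4375 = 7.03 |
| DEC2021 | 14JAN2022 | 14JAN2022 | 31DEC2021 | 14 | 228/30.4375 = 7.49 vs 214/30.4375 = 7.03 |
| OCT2021 | 15MAR2022 | 15MAR2022 | 31OCT2021 | 135 | 288/30.4375 = 9.46 vs 153/30.4375 = 5.03 |

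In the first row, last dose plus 90 days moves from 28 February 2022 to 12 April 2022, again 43 days. Each excess is a minimum error, because the true dose may have been earlier in the recorded month.

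**Controls.** The rule works where it should:

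- NOV2021 with reference 10DEC2021 gives 30NOV2021.
- JAN2022 with reference 10JAN2022 gives 10JAN2022.
- Year 2021 alone with reference 10JAN2022 gives 31DEC2021.

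Setting the last control beside DEC2021 with reference 10JAN2022, which gives 10JAN2022, shows that the added month makes the answer worse. Only the change of calendar year breaks the rule.

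**The case against.** The strongest objection is that this may never arise. Doses are given under supervision, the date and time of each go into the source and the CRF (Protocol 6.4), and each injection has its own CRF record (Protocol Appendix 9). A final dose with a missing day, a known month, and EOT or death in a later year should be rare. That stands, and the documents give no count.

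The second objection concerns size. The Schedule of Activities puts the EOT visit within 14 days of the final dose, so on schedule the excess over month end is at most 14 days, and the 43-day example needs a late EOT. This limits the usual size but does not cap it. The SAP defines last dose as the latest nonzero dose (SAP 3.4), and Protocol 6.6.2 allows treatment interruptions of up to 4 weeks before discontinuation is called for. EOT can therefore fall more than 14 days after the last nonzero dose.

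The third concerns the downstream effects, and these qualifications also stand:

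- The on-treatment period lengthens only if new anticancer therapy has not already ended it.
- Active adverse event collection runs for a minimum of 90 days from the actual last dose (Protocol 8.3.1), so a longer window may find few further events.
- An effect through the imputed start of new therapy needs that date to be incomplete too. Last dose must also decide the result against the PD date and the therapy end date.
- Counting more adverse events and deaths is the cautious direction for safety.

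Finally, SAP 5.3 requires imputed values to be flagged in listings, so an affected date would be visible. None of this makes the imputed date correct.

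**Conclusion.** The concern holds. As written, SAP 5.3.3.2 returns a date outside the recorded month whenever month and year are known and the year is before that of the earlier of EOT and death. The parallel rule in SAP 5.3.3.4 has the missing branch and no reason is given for the difference, so this looks like a drafting omission.

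The excess over month end is at most 14 days when the EOT visit is on schedule, and larger when EOT or death comes late: 43 and 135 days in the illustrations. Treatment duration is overstated by the full excess. The 90-day death window lengthens equally, and the on-treatment period by up to that much, depending on new therapy. ORR, the primary endpoint, is not directly affected.

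The number of participants affected cannot be derived from the documents and is probably small. Treatment does cross year ends: enrolment closed in January 2022 and treatment continues until confirmed progression or another stopping reason. This is a minor correction, worth making because the algorithm will be coded as it stands.

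**What to change.** Replace the same-year condition in the second branch with a year-month comparison: *last day of the recorded month, when the recorded year and month precede the year and month of the earlier of EOT and death*. The other two branches stay as they are. Every case now handled correctly gives the same result, and the section then agrees with SAP 5.3.3.4.

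The cost is one clause in the SAP and one line of code. If the SAP is not reopened for another reason, the corrected rule can be applied in programming and recorded in the CSR as a deviation, as SAP Section 2 provides. A check for partial last-dose dates spanning a year end would show whether any participant is affected.
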